1.2.3 PCLX-001 Pharmacokinetics and Pharmacology

Mouse Pharmacokinetics

PCLX-001 was dosed as a bolus solution intravenously at 3 mg free base/kg (5% DMSO; 95% sterile water) or by gavage orally as a solution at 10 mg free base/kg (5% DMSO; 40% PEG400; 55% sterile water) to female NMRI mice (n=3/dose route). Blood samples (10 µL) were taken from each mouse at 5 (IV only), 15, 30 minutes, 1, 2, 4, 6 and 8 hours post-dose, mixed with two volumes of distilled water and stored frozen until analysis.

Following intravenous administration at 3 mg free base/kg, PCLX-001 mean blood clearance was low at 3mL/min/kg (~3% liver blood flow), mean volume of distribution (V_{ss}) was low at 0.4 L/kg, resulting in a moderate mean half-life at 1.6 hours. Mean AUC_{0-8} was 1,119,500 ng·min/mL.

Following oral administration at 10 mg free base/kg, PCLX-001 had a mean C_{max} of 11,200ng/mL and median t_{max} at 2 hours. Mean AUC_{0-8} was 3,400,810 ng·min/mL and mean bioavailability recorded at 91%.

PCLX-001 was not brain penetrant in mouse models (B:B ratio following a 1 mg/kg IV dose is 0.04 at 5- and 30-minutes post-dose).

Rat Pharmacokinetics

PCLX-001 was dosed as a bolus solution intravenously at 1 mg free base/kg (5% DMSO; 95% saline) or by gavage orally as a solution at 3 mg free base/kg (5% DMSO; 95% sterile water) to male Sprague Dawley rat (n=2 IV; n=3 PO). Blood samples (10 µL) were taken from each rat at 5 (IV only), 15, 30 minutes, 1, 2, 4, 6 and 8 hours post-dose, mixed with two volumes of distilled water and stored frozen until analysis.

Following intravenous administration at 1 mg free base/kg, PCLX-001 mean blood clearance was low at 15 mL/min/kg (~18% liver blood flow), mean volume of distribution (V_{ss}) was moderate at 1.3 L/kg, resulting in a moderate mean half-life at 1 hour. Mean AUC_{0-8} was 67,230 ng·min/mL. Blood clearance was well aligned to hepatic extraction (E_H) at 16%, determined from a separate male Sprague Dawley rat hepatic portal vein study following oral dosing at 3 mg free base/kg.

Following oral administration at 3 mg free base/kg, PCLX-001 had a mean C_{max} of 170ng/mL and median t_{max} at 4 hours. Mean AUC_{0-8} was 52,868 ng·min/mL and mean bioavailability 26%.

Dog Pharmacokinetics

PCLX-001 was dosed as a bolus solution intravenously at 1 mg free base/kg (in saline) or by gavage orally as a solution at 10 mg free base/kg (in saline) to male beagle dog (n=3/dose route). Blood samples (10 μ L) were taken from each dog at 5, 15, 30 minutes, 1, 2, 4, 6, 8 and 24 hours post-dose, mixed with two volumes of distilled water and stored frozen until analysis.

Following intravenous administration at 1 mg free base/kg, PCLX-001 mean blood clearance was moderate at 22 mL/min/kg (~58% liver blood flow), mean volume of distribution (V_{ss}) was moderate at 4.3 L/kg, resulting in a moderate mean half-life at 2.3 hours. Mean AUC_{0-24} was 42,140 ng.min/mL.

Following oral administration at 10mg free base/kg, PCLX-001 had a mean C_{max} of 1229ng/mL and median t_{max} at 1.7 hours. Mean AUC_{0-24} is 560,220 ng.h/mL and mean bioavailability was 133%.

Pharmacokinetics Interpretation

The low volume of distribution observed in mouse (less than body water) appeared to be a mouse specific phenomenon. Improved efficacy may be seen in higher volume species through better distribution to the target such that there is no net change in potential therapeutic index.

In vitro ADME Profile

PCLX-001 (0.5 μ M) has low intrinsic clearance (Cl_{int}) in mouse, rat and human when incubated with liver microsomes, with Cl_{int} of <0.5, 1.0 and 0.7 mL/min/g respectively (using 52.5 mg microsomal protein/g liver). Cl_i in mouse and rat is consistent with the low *in vivo* Cl_B observed. Blood:plasma ratio was 0.59, 0.56, 0.69 and 0.50 in mouse, rat, dog and human respectively.

PCLX-001 has high (>99%) plasma protein binding in mice, rat, dog, and human plasma after 4 hour incubation at 5 μ M.

The cytochrome P450 enzymes (CYP) are a super family of hemethiolate enzymes responsible for the metabolic clearance of a wide variety of drugs. To characterize the metabolic clearance of PCLX-001, the relative contribution of CYP450 enzymes to the overall elimination process and the identification of the enzymes responsible for oxidative reactions were studied using native recombinant human CYP enzymes. These studies showed that PCLX-001 directly inhibited CYP3A4 (IC₅₀ of 12.1 μ M), CYP1A2 (40.6 μ M), CYP2B (63.02 μ M), CYP2C9 (52.3 μ M), and CYP2C19 (60.7 μ M). There was no inhibition of CYP2D6, CYP2E1, CYP2A6, or CYP2C8 (all with IC₅₀ > 100 μ M).

PCLX-001 is a substrate for P-glycoprotein, as demonstrated by efflux studies in CaCo2 cells. It is not a substrate for or OAT1, OAT3, OCT1, OCT2, OATP1B1, OATP1B3, MATE1, MATE2K or BRCP. Overall, PCLX-001 shows a low probability for drug-drug interaction.

PCLX-001 was not mutagenic in the Ames test.

In vitro hERG Testing

A non-GLP study was done by a group developing a proprietary system for human ether-á-go-go-related (hERG) analysis (<https://www.achlys-inc.com/Cardiomyocytes>). The negative controls were acetylsalicylic acid and chloramphenicol and the positive control (determined IC₅₀ of 0.9 μ M) was Thioridazine Hydrochloride. PCLX-001 had a determined IC₅₀ of 9.9 μ M. This concentration was well above that expected to be achieved in a human phase I trial and suggests that PCLX-001 is likely not to be cardiotoxic.

KINOMEscan

PCLX-001 is a small molecule inhibitor that theoretically could also have the ability to inhibit kinases, and cause unexpected off-target effects. PCLX-001 was screened *in vitro* at concentrations of 0.5, 10, and 100 μ M (269, 5380, and 53,800 ng/mL) for its ability to inhibit the activity 468 human kinases. PCLX-001 at concentrations up to 10 μ M (5380 ng/mL) did not inhibit any kinase. PCLX-001 at 100 μ M (53,800 ng/mL), a concentration ~4000 x greater than the EC50 of PCLX-001 for BL2 cells, produced meaningful inhibition of only three kinases: MRCKA, PIP5K2B, and SRPK1. Based on these results, PCLX-001 is unlikely to produce adverse effects in patients due to off-target kinase inhibition and appears to be NMT-specific.

1.2.4 PCLX-001 Toxicology and Safety Profile

Non-GLP Toxicity and Safety Profile:

Tissue of control and PCLX-001 treated (with doses up to 50 mg/kg subcutaneous daily injection) NOD/SCID mice were studied after formalin fixation and paraffin-embedding, followed by immunohistochemical staining. There was no morphologic evidence of toxicity of PCLX-001 on small intestine, kidney, liver, or bone marrow. Blood counts and standard biochemical testing of blood from treated and untreated mice revealed no evidence of marrow, renal, or hepatic toxicity.

PCLX-001 is >90% orally bioavailable in mice and dogs and 26% in rats, has a half-life from oral dosing of 10 mg/kg of 5.7 hours in mice and 3.9 hours in dogs, and is well-tolerated by mice, rats, and dogs with a maximum tolerated dose in 14-day repeat dose toxicity studies of >75 mg/kg in rats and 4 mg/kg in dogs. Based on a body surface area scaling of the 50 mg/kg dose that resulted in complete tumor remission in most mouse xenografts of hematologic malignancies (BL, DLBCL, AML), the effective human dose is projected to be ~4 mg/kg daily (250 mg for a 70 kg individual).

GLP Non-Clinical Safety Testing:

PCLX-001 was evaluated for safety in 4-week oral toxicity studies with 2-week recovery periods in rats at 50, 125, and 300 mg/kg/day and dogs at 2, 4, 8, and 12 mg/kg/day, performed to GLP standards (Weickert *et al*, 2020). The highest non-severely toxic dose levels (HNSTDs) were 125 mg/kg/day for male rats, 300 mg/kg/day for female rats, and 4 mg/kg/day for dogs of both sexes. At higher dose levels, dose-limiting toxicity occurred within the first few days, was similar in both species, and was attributed to GI mucosal damage and decreased hematopoiesis, with secondary complications such as dehydration and inflammation.

In dogs, systemic exposure to PCLX-001 increased more-than-proportionally with dose level after the first dose and did not change with repeated daily dosing. After the last dose at the HNSTD, C_{max} averaged 651 ng/mL and 24-hour AUC averaged 3,760 h*ng/mL. In rats, systemic exposure to PCLX-001 after the first dose increased approximately proportionally with dose level and was much greater in males than females at all dose levels. With repeated daily dosing, exposure decreased dramatically in male rats but less so in female rats. As a result, exposure to PCLX-001 was similar in rats of both sexes after the last dose. After the last dose at the HNSTD in males and females, C_{max} was 1650 and 8510 ng/mL, respectively, and 24-hour AUC averaged 6470 and 7590 h*ng/mL, respectively. When expressed on the basis of body surface area, the HNSTDs in male rats, female rats, and dogs were 750, 1800, and 80 mg/m², respectively.

As recommended in the ICH S9 Guidance, the starting human dose level of 20 mg/m² would be appropriate since this approximates 1/6th of the HNSTD in dogs

In rat and dog GLP studies, there were no coagulation toxicities noted with PCLX-001. Similarly, no significant cardiac findings were elicited in dogs. ECGs at baseline were similar to those after 4 weeks of dosing or at the end of the recovery period.

1.3 Study Rationale

1.3.1 Rationale for Patient Selection in Dose Escalation

Patients selected for study have relapsed/refractory B-cell lymphomas and advanced solid tumors who have failed or are not eligible for therapies expected to provide clinical benefit. This protocol will not include patients with leukemia for which an independent phase I study is planned.

Given the strong *in vitro* and *in vivo* single-agent antitumor activity and tolerability of PCLX-001, it is hypothesized that in this first-in-human trial, PCLX-001 will be safe, tolerable and demonstrates preliminary clinical activity in human patients with specified relapsed/refractory (R/R) non-Hodgkin lymphoma (NHL) and advanced solid malignancies.

Pacylex Pharmaceuticals, Inc. will not study PCLX-001 in a pediatric population in this initial phase I study. As this is a novel agent and target, Pacylex Pharmaceuticals, Inc. will consider pediatric and adolescent patients once safety has been adequately established in adult patients.

1.3.2 Rationale for Patient Selection in Dose Expansion

PCLX-001 has been studied in a number of pre-clinical studies, and these data provide justification for the selected patient population.

Solid tumors: Selected by pre-clinical sensitivity in cell lines

Three large tumor cell line robotic screens have been performed with PCLX-001, as well as several cell line derived murine xenograft studies as well as patient derived murine xenograft studies. In aggregate, these data suggest sensitivity in breast, non-small cell lung, small-cell lung, colorectal, and bladder cancers (Figure 4).

[figure not shown]

Figure 4. Breadth of efficacy screen demonstrates that PCLX-001 is active against various other cancer cell lines including those derived from solid tumors. Absolute IC₅₀ values of various cell lines treated for 3 days (A, B) or 6 days (C, D) with 0.0005 - 10 μM PCLX-001. Cell lines are arranged according

cancer type. Individual bars represent a single cancer cell line derived from B cell lymphoma and Mantle Cell Lymphoma, Acute Myeloid Leukemia (AML), Breast, Small-cell lung carcinoma (SCLC), Non-small-cell lung carcinoma (NSCLC). ChemPartner robotic platform determined cell viability using Cell Titer Blue viability assay.

Further evidence of solid tumor activity is provided by murine models of human lung and breast cancers (Figure 5).

[figure not shown]

Figure 5. PCLX-001 inhibits tumor growth in patient derived small cell lung cancer and breast cancer xenograft models. Established tumor in patient derived xenografts grown in immunodeficient mice were treated with daily PCLX. Panel A shows oral therapy of a small-cell lung cancer patient derived xenograft, showing efficacy superior to that of cisplatin. Panel B shows the efficacy of subcutaneous PCLX-001 in a cell line derived breast cancer model.

B-cell Lymphomas

In three large tumor cell line robotic screens, PCLX-001 potently and preferentially inhibited the growth of hematological cell lines, including B-cell lymphomas, in comparison to other types of cancer cell lines. Moreover, PCLX-001 selectively killed lymphoma cells while sparing normal cells *in vitro*, as well as in three human lymphoma xenograft models including a patient-derived, drug-resistant tumor. The global myristylation of lymphoma cell proteins, including that of the protein tyrosine kinase Src, was found to be especially sensitive to PCLX-001 treatment. This was accompanied by the loss of Src localization to the cell membrane and the targeting of Src, as well as other SFKs, for degradation by the proteasome. Without functional SFKs (especially Lyn-SFK), pro-survival signaling downstream of the B-cell receptor (BCR) was profoundly attenuated in all B-cell lymphoma cell lines, resulting in apoptosis.

Of potential therapeutic relevance, the effects of PCLX-001 on BCR signaling and lymphoma cell survival were more potent than those of dasatinib and ibrutinib, two clinically approved drugs. By inhibiting critical signaling processes immediately downstream of the BCR, PCLX-001 mediated NMT inhibition may provide an effective, selective and novel therapeutic approach for treatment of B-cell lymphoma.

NMT1 and NMT2 Expression

NMT1 number of transcripts is about eight times the number of *NMT2* transcripts in all cell lines. As well, there is a heterogeneous but significant reduction of *NMT2* expression or low levels of *NMT2* protein in cancer cell lines, and particularly in hematological cancers. This may account for these tumours being more sensitive to PCLX-001.

NMT2 deficiency has been identified in a high proportion of human tumors interrogated with immunohistochemistry using a *NMT2* mAb. Normal breast epithelial elements in 10 normal breast mammoplasty specimens were universally *NMT2* positive (1-2+) on a 0-3 scale (scored as 0 – absent; 1+ weak staining; 2+ moderate staining; 3+ strong staining). Primary breast adenocarcinoma samples from participants in the BCIRG 001 clinical trial were studied using 1.0 mm tissue microarrays with triplicate samples for each tumor. *NMT2* immunohistochemistry status in malignant cells was scored as 0 absent; 1+ weak staining; 2+ moderate staining; 3+ strong staining. *NMT2* status was generally homogeneous within each core and concordant across triplicates. 509 of the 706 breast cancer adenocarcinomas were *NMT2* negative. Using identical techniques, 157 of 214 (73%) of non-small cell lung carcinomas, and 23 of 23 colon cancers were *NMT2* deficient by immunohistochemistry. Preliminary data from a series of bladder urothelial carcinomas show a significant proportion lack detectable *NMT2* protein.

Altogether, the reduction in *NMT2* expression in hematological cancer cell line and the solid tumours described may be more prone to growth inhibition.

Populations for Expansion Cohorts

Based on the pre-clinical sensitivity in cell lines and molecular markers associated with PCLX-001 sensitivity, it is hypothesized that an expansion cohort of solid tumors of breast, non-small cell lung, small-cell lung, colorectal, and bladder origin would be particularly susceptible. These patients will comprise Expansion Cohort A.

Also, an expansion cohort of relapsed/refractory B-cell lymphomas will be studied. Patients with diffuse large B-cell lymphoma (including transformed DLBCL), high grade B-cell lymphoma (HGBL), follicular lymphoma, mantle cell lymphoma, and Burkitt lymphoma would similarly be expected to be sensitive to PCLX-001. These patients will comprise Expansion Cohort B.

2. OBJECTIVES

The primary objectives of this study are to:

- Assess safety and tolerability of oral PCLX-001 in patients with B-cell lymphoma and advanced solid tumours
- Determine the maximum tolerated dose (MTD) and / or recommended Phase II dose (RP2D) of PCLX-001 in patients with B-cell lymphomas and advanced solid tumours
- Evaluate the pharmacokinetics (PK) of PCLX-001 in patients with B-cell lymphomas and advanced solid tumours

The secondary objective of the study is to:

- Evaluate the preliminary single agent anti-tumour activity of PCLX-001 in the patient populations studied

The exploratory objective of this study is to:

- Assess the pharmacodynamic (PD) effects of PCLX-001 in patients with B-cell lymphomas and advanced solid tumours

3. STUDY DESIGN

3.1 Overview of Study Design

This is a phase I dose-escalation, safety and tolerability study of oral PCLX-001, conducted in a multicenter, non-randomized, open-label, non-controlled design. The study is comprised of two parts: Part A (single-agent dose escalation) and Part B (single-agent expansion cohorts).

For Part A dose-escalation, patients will be accrued in cohorts of 3 to 6 patients to each dose level. A new dose level cannot open to accrual until toxicity has been determined in the preceding dose level (i.e. all patients have completed their first cycle of therapy and data for all patients in that dose level have been reviewed at a safety cohort review meeting). Six patients will be treated at the maximum tolerated dose (MTD) and/or recommended phase II dose (RP2D). If required, the MTD cohort may be expanded by an additional 10 patients for further toxicity and response assessment. The MTD cohort expansion may be restricted to B-cell lymphoma or advanced solid tumours to ensure there is proper distribution during dose escalation.

For Part B (single agent expansion cohorts), two expansion cohorts (N=20 each) will be opened to determine the preliminary clinical activity of PCLX-001. The Part B dose expansion Cohort A will occur once MTD and RP2D has been determined. Part B dose expansion Cohort B will occur once dose escalation has achieved a dose that has both acceptable safety and achieves drug exposures predicted to have activity in R/R B-cell lymphomas.

Expansion Cohort A: Participants with advanced solid malignancies showing preclinical sensitivity or molecular markers of sensitivity to PCLX-001. This includes breast, non-small cell lung (NSCLC), small-cell lung (SCLC), colorectal (CRC), and bladder cancers

Expansion Cohort B: Participants with relapsed/refractory (R/R) B-cell lymphoma: diffuse large B-cell lymphoma (DLBCL), high grade B-cell lymphoma (HGBL), follicular lymphoma (FL), mantle cell lymphoma (MCL), and Burkitt lymphoma. Transformed large B-cell lymphoma will also be included.

3.1.1 Selection of Starting Dose Level and Dosing Considerations

As recommended by the ICH S9 Guidance, the starting dose level is 1/6th the highest non-severely toxic dose (HNSTD) from GLP studies in the most sensitive of tested non-rodent species. The HNTSD was 4 mg/kg/day for dogs of both sexes and, when expressed as body surface area, this calculates to 80 mg/m². Consequently, the starting dose level in humans would be approximately 20 mg/m². To ensure maximal safety in this first-in-human trial, the starting dose level was chosen to be 20 mg daily. PCLX-001 will be supplied as 10 mg and 70 mg capsules which provides the range of doses required for dose escalation.

3.2 Definition of Dose Limiting Toxicity and Maximum Tolerated Dose

Toxicities are to be graded according to the National Cancer Institute Common Terminology Criteria for Adverse Events (NCI CTCAE, Version 5.0). A copy of the CTCAE version 5.0 can be downloaded from the CTEP home page (<http://ctep.cancer.gov>).

Dose Limiting Toxicity (DLT) for Part A, dose-escalation, is defined as any of the following AEs related to PCLX-001 treatment occurring in Cycle 1:

Hematologic

- Grade 4 thrombocytopenia (platelet count < 25 x 10⁹/L)
- Grade ≥ 3 thrombocytopenia (platelet count < 50 x 10⁹/L) associated with any major bleeding, and/or requirement for transfusion
- Grade 4 neutropenia (ANC < 0.5 x 10⁹/L) for ≥ 7 days^a
- Febrile neutropenia. (Per NCI CTCAE, ANC < 1.0 x 10⁹/L and fever ≥ 38.3°C or a

sustained temperature of $\geq 38^{\circ}\text{C}$ for more than one hour). Febrile neutropenia is by definition a grade ≥ 3 toxicity.

^a Detection of CTCAE Grade 4 neutropenia (only in Cycle 1) will trigger twice-weekly white blood cell counts to be performed, and will be considered a DLT if drug interruption lasts ≥ 7 days.

Non-hematologic

Any non-hematological toxicity of CTCAE Grade ≥ 3 is considered a DLT, excluding the following:

- Grade ≥ 3 nausea, vomiting and diarrhea which are controlled with anti-emetics and/or other supportive care within $\leq 72\text{hr}$
- Brief (i.e. lasting ≤ 72 hours) CTCAE Grade 3 fatigue
- Alopecia of any grade
- Isolated, asymptomatic, biochemical laboratory values including electrolyte abnormalities, above or below normal reference ranges, which are judged not clinically significant by the Investigator
- Miscellaneous
- Any patient meeting Hy's law of drug-induced hepatic injury (AST or ALT >3 times ULN with bilirubin 2 times ULN; absence of initial cholestasis with ALP >2 times ULN; no other explanation) is considered a DLT.
- Any toxicity thought to be related to study drug that, at the discretion of the investigator, or his/her designated associate(s), is thought to warrant withholding the drug may be declared as a DLT. Such toxicities might for example be CTCAE Grade 1 or CTCAE Grade 2 toxicities that interfere with the activities of daily life, such as long-lasting fatigue, or anorexia, making a dose reduction necessary in order to ensure the patient's compliance.
- Any toxicity thought to be related to study drug which requires interruption of oral PCLX-001 for longer than 28 consecutive days from the time of scheduled dosing will be declared as a DLT.

In rare instances, an event may fall within the definition of a DLT as defined above but the event may not be considered dose-limiting (i.e. not clinically meaningful/significant). If this occurs, a meeting with investigators and sponsor will take place to thoroughly review the event, supporting data and reasons for not considering the event a DLT. This will be clearly documented with supporting rationale. Conversely, other events may occur which do not meet the definition of a DLT but are sufficient concern to the investigators and sponsor to be considered a DLT.

Maximum Tolerated Dose (MTD) is defined as the highest dose tested in which fewer than 33% of patients experienced DLT attributable to the study drug(s), when at least six patients were treated at that dose and are evaluable for toxicity. The MTD is one dose level below the lowest dose tested in which 33% or more patients experienced DLT attributable to the study drugs. At least six patients will be treated at the MTD.

Dose escalation and determination of the MTD will be based on the occurrence of DLT's in cycle 1. Patient safety will be monitored on an ongoing basis during this study. If cumulative toxicities are seen in subsequent treatment cycles, a decision regarding modification or discontinuation of the study drug and/or patient enrollment will be made by the investigator in consultation with the sponsor.

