3.4 Part A Dose Escalation Schedule and Treatment Schema

Oral PCLX-001 will be provided as continuous daily dosing on a 28-day cycle. The starting dose of PCLX-001 will be 20 mg daily (Section 3.1.1). Dose escalation will follow a modified Fibonacci design such that the magnitude of escalation decreases as the dose level nears the human equivalent dose (HED) of the HNSTD in dogs and then escalate at 1.4 times the previous dose until MTD or RP2D is reached.

The dose level schedule is as below (1 cycle = 28 days):

Dose Level**	Daily Oral Dose (mg)	Number of Capsules	
		10 mg	70 mg
-1	10	1	0
1 (starting dose)*	20	2	0
2	40	4	0
3	70	0	1
4	100	3	1
5	140	0	2
6	210	0	3
7	280***	0	4

* Trial will start at Dose Level 1 and will de-escalate to Dose Level -1 if DLT is observed.

** If ≥ 2 out of 6 DLTs are observed in Dose Level -1, 1 or 2 then consideration will be given to changing dosing schedule (eg. 28-day schedule with each week comprising 4 days on medication and 3 days off medication).

*** If DLT is not observed at the dose of 280 mg, the dose will be considered the MTD. If required, the MTD cohort may be expanded by an additional 10 patients for further toxicity and response assessment.

For each dose-escalation cohort, treatment with the first dose of PCLX-001 will be staggered such that the second participant enrolled in the cohort will receive PCLX-001 at least two weeks after the first participant and all subsequent participants at least one week after the previous participant.

Each participant will be treated with the dose of PCLX-001 they are assigned to, until the occurrence of a DLT or other study stopping point occurs, at which point the dose of PCLX-001 will be modified as per protocol or study drug administration will be discontinued.

If DLT occurs at Dose Level 1, a safety meeting will occur to determine the feasibility of continuing the study at Dose Level -1. Alternative dose schedules may also be considered if DLTs occur during Dose Levels, -1, 1 or 2.

Participants who experience a DLT or have received at least 21 days of PCLX-001 during cycle 1 will be evaluable for toxicity. If a participant does not meet these criteria, the participant may be replaced (Section 4.3).

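### The Grade 4 neutropenia DLT in Section 3.2 has two non-equivalent tests; more narrowly, the over-28-day interruption DLT can be met only after Cycle 1, and no text says whether it then counts as a Cycle 1 DLT

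*Combined protocol and SAP*

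**What the plan says.** **Neutropenia.** Section 3.2 of the protocol says that a Part A DLT "is defined as any of the following AEs related to PCLX-001 treatment occurring in Cycle 1". One item in the hematologic list is "Grade 4 neutropenia (ANC < 0.5 x 10⁹/L) for ≥ 7 days". Footnote a to that item says that Grade 4 neutropenia found in Cycle 1 leads to twice-weekly white-cell counts, "and will be considered a DLT if drug interruption lasts ≥ 7 days". Footnote g of Table 7B repeats the extra counts and links them to the DLT decision, without mentioning interruption.

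**Interruption.** Section 3.2 also says that a drug-related toxicity that "requires interruption of oral PCLX-001 for longer than 28 consecutive days from the time of scheduled dosing will be declared as a DLT". Under Section 3.4, dosing is daily and continuous and a cycle is 28 days.

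**Counting rules.**
- Section 3.1: "A new dose level cannot open to accrual until toxicity has been determined in the preceding dose level", which it explains as all patients having finished Cycle 1 and their data having been reviewed.
- Section 3.4: "Participants who experience a DLT or have received at least 21 days of PCLX-001 during cycle 1 will be evaluable for toxicity". Otherwise: "If a participant does not meet these criteria, the participant may be replaced".
- Section 4.3: replacement is mandatory below 21 days of drug, but a patient who stops because of a Cycle 1 DLT is not replaced.
- Section 5.5: 21 days of the planned dose are required unless a DLT occurs.
- Section 8.2: the MTD-determining population is defined by adherence to the regimen and completed safety evaluations, or by earlier discontinuation for a DLT. It has no 21-day threshold.

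**The concern.** The 3+3 rule acts on counts of DLTs among three or six patients, so whether a patient has a DLT must follow from the text. For Grade 4 neutropenia it does not: the list item and its footnote can give opposite answers for the same patient. The event is foreseeable, because Section 1.2.4 attributes dose-limiting toxicity in both animal species partly to decreased blood-cell production.

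The interruption criterion raises a timing question. It is mandatory, and escalation and the MTD rest on Cycle 1 DLTs, yet it needs more consecutive days without drug than Cycle 1 can hold. A patient's status could therefore change after the decision that used it.

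**Working it through.** **1. The plan's own threshold.** Section 3.2 requires a DLT proportion below 33% in at least six evaluable patients at the MTD. 1/6 = 16.7% passes and 2/6 = 33.3% does not, which agrees with the escalation table in Section 3.3.

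**2. The two neutropenia tests side by side.**

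| Patient in Cycle 1 | List item | Footnote a | Either suffices | Both needed |
|---|---|---|---|---|
| Grade 4 for 3 days, hold of 8 days | no DLT | DLT | DLT | no DLT |
| Grade 4 for 7 days or more, hold under 7 days | DLT | no DLT | DLT | no DLT |

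The four possible readings give four different columns, and no section selects one.

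**3. Effect of one reclassified patient (Section 3.3).**
- 0/3 (escalate) becomes 1/3 (add three patients).
- 1/3 (add three) becomes 2/3 (stop).
- 1/6 (escalate) becomes 2/6 (stop).

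**4. When the interruption criterion is met.** Take one unbroken hold with the first missed dose on Day k and no earlier missed dose. Days of drug = k − 1. The 29th consecutive missed day, the first beyond 28, is Day k + 28.

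| First missed dose (k) | Days of drug in Cycle 1 | Criterion met | Default status before then |
|---|---|---|---|
| Day 2 | 1 | Day 30 | replaced |
| Day 21 | 20 | Day 49 | replaced |
| Day 22 | 21 | Day 50 | evaluable, no DLT by this rule |
| Day 28 | 27 | Day 56 | evaluable, no DLT by this rule |
| Day 29 (scheduled Cycle 2 Day 1) | 28 | Day 57 | evaluable, no DLT by this rule |

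No more than 27 doses can be missed within Cycle 1 (Days 2 to 28), so the criterion is never met inside it. The last row also applies if the count always runs from the scheduled start of Cycle 2. The wording permits that reading, and Section 3.6 uses a similar limit for delayed cycles.

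**5. Holds begun on Day 2 to 21.** Reaching 21 days of drug becomes impossible at the 8th missed dose (28 − 8 = 20), on Day k + 7. A replacement starting on Day k + 8 finishes Cycle 1 on Day k + 8 + 27 = k + 35. That is 7 days after the held patient meets the criterion on Day k + 28, so the information arrives before review.

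**6. Holds begun on Day 22 to 28, or a delayed Cycle 2.** Under the stagger in Section 3.4, patient 2 starts at least 14 days after patient 1, and patient 3 at least 7 days after patient 2. In a cohort of three at minimum spacing, patient 3 reaches Day 28 on patient 1's Day 28 + 21 = 49 and on patient 2's Day 28 + 7 = 35. The criterion is then met this long after the whole cohort has finished Cycle 1:

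| Patient | Hold begun Day 22 to 28 (met Day 50 to 56) | Counted from Cycle 2 Day 1 (met Day 57) |
|---|---|---|
| 1 | 1 to 7 days | 8 days |
| 2 | 15 to 21 days | 22 days |
| 3 | 22 to 28 days | 29 days |

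Section 11.2 sets a deadline for data (7 working days), not a review date. It also refers to the start of Cycle 2 dosing, which a held patient may not have reached.

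**7. Who could be in this position.** Toxicities that are already DLTs by grade do not depend on the criterion. For a delayed Cycle 2, an example is an afebrile ANC of 0.5 to below 1.5, or platelets of 25 to below 75 (x 10⁹/L) without major bleeding or transfusion. Neither is a listed DLT, but Section 5.3.2 bars Cycle 2 Day 1 dosing at those counts.

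**The case against.** The strongest reply is that the plan already handles both cases. Section 3.2 lets the investigator declare a DLT for a drug-related toxicity judged to warrant withholding drug, with Grade 1 and 2 examples. It also lets investigators and sponsor count an event outside the list, or decline one inside it. Section 10.3 requires safety meetings before escalation. Section 10.5 pauses accrual for any drug-related SAE or Grade ≥3 AE, so every drug-related Grade 4 neutropenia is reviewed centrally. On timing, the Cycle 1 limit attaches to the adverse event, which can begin in Cycle 1 and be confirmed later.

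Much of this stands. The interruption criterion is not void; it is confirmed late. A reader might infer that a patient on hold has no classification at cohort review. The documents do not support that: Sections 3.4, 4.3 and 5.5 give a default status, a patient with a DLT is evaluable, and judgement can be applied. Step 5 also removes most early holds from concern, and the stagger removes part of the rest for patient 1.

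What remains is that discretion permits a classification without defining one, while the interruption rule is mandatory. Section 10.5 settles SAE causality and re-opening of accrual; it contains no DLT rule. If either neutropenia test suffices, the ambiguity errs toward caution, but the plan does not say so.

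**Conclusion.** The neutropenia conflict is established by the text and is the main point: two tests, opposite answers for an ordinary case, and one patient is enough to change the escalation action.

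The interruption point is secondary. No text says whether a DLT confirmed after Cycle 1 is assigned back to it. The practical exposure is a patient with at least 21 days of drug whose hold began on Day 22 to 28, or whose Cycle 2 is delayed, chiefly if enrolled later in the cohort. That patient can be counted as evaluable without a DLT and meet the criterion afterwards. The day counts assume one unbroken hold and no earlier missed dose; step 6 also assumes three patients at minimum spacing.

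A reader might go further and infer that the MTD will be biased. The documents give no frequency for either event and fix no review date, so no shift in escalation probability can be claimed.

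**What to change.** 1. Reconcile the neutropenia item and footnote a in Section 3.2 to one stated criterion, or state that either suffices. Make footnote g of Table 7B match.
2. In Section 3.2, state the day from which the over-28-day interruption is counted and whether a DLT confirmed after Cycle 1 counts as a Cycle 1 DLT.
3. State how a patient still on a drug-related hold is counted at cohort review, and align Sections 3.1, 3.4, 4.3 and 8.2 with that, including mandatory versus optional replacement.

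Which clinical criterion to adopt is for the sponsor. The cost is protocol wording, and possibly an occasional later cohort review.
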